5.8 Study Materials

Astra-Zeneca (AZ) will provide saxagliptin and matching placebo at no cost for this study.

5.9 Safety Assessments

Study drug toxicities will be assessed continuously. Adverse events will be evaluated on a continuous basis while the patient is on study and until 30 days after the last dose of study drug. Patients should be followed until all treatment-related adverse events have recovered to baseline or are deemed irreversible by the principal investigator.

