Exclusion Criteria:	
Patients with:
 
 1. Contraindications for moderate exercise 2. Implanted devices (e.g., pacemakers) that may interact with Tanita scale 3. Previous coronary or cerebrovascular event within 6 months of screening or active or clinically significant coronary and/or peripheral vascular disease 4. Low hematocrit (< 28 UNITS). 5. Pre-existing liver disease and/or ALT and AST $>2.5 \times$ UNL 6. Kidney disease at levels defined by: serum creatinine levels ≥ 1.5 mg/dL for men, ≥ 1.4 mg/dL for women, estimated CrCl ≤ 50 mL/min 7. History of pancreatitis, or cancer (except basal cell carcinoma) 8. Statin use started (or dose change) in the last 3 months, 9. Use of oral or injectable anti-diabetic medication other than Metformin 10. Daily use of a consistent long-term steroid medication (oral, inhaled, injected) within the last 3 months 11. Systolic BP > 140 mmHg and Diastolic BP > 90 mmHg at screening visit. 12. Active wounds or recent surgery within 3 months. 13. Inflammatory disease, or chronic current use of anti-inflammatory drugs within the last 3 months. 14. triglycerides >400 mg/dL 15. untreated hyper/hypothyroidism 
Additionally, patients who are active smokers, patients who are pregnant, nursing women, and post-menopausal women who are on hormone replacement therapy will be excluded.
 
Patients on low dose oral contraceptives will be allowed to participate as these formulations contain lesser amount of estrogens.

----------------------------	---

Criteria for Evaluation: (Efficacy, safety, stopping rules, etc.)	Subjects will be screened at week -4, then evaluated for end points at weeks 0, 6 and 12. Study participation will be stopped for adverse effects at the discretion of the study investigator. Subjects may stop study participation at any time and for any reason.
Statistics:	The total sample size requested, accounting for attrition over the 12-week period, is 20 subjects per group or 40 subjects total. Sample size estimates were based on the effects of exercise on CD34+/KDR+ cells as described in the literature. The effect of a single session, as well as extended training, on healthy subjects or those with existing cardiovascular conditions appears to increase the CD34+/KDR+ cells. This will provide 73% power (see statistics section). A p-value of less than 0.05 will be considered statistically significant.

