4 INVESTIGATIONAL PLAN

4.1 Study Design and Duration

Study Schema, 42 Type 2 diabetic Subjects Aged 40-70 on stable dose of Metformin

+/- 3 days for visits Wk 0 Wk 6 and Wk 12, if the particular day is not feasible

*Assessed at week 0, 6 and 12: Biochemical and cellular markers of endothelial function and Pulse wave analysis and velocity (PWA and PWV).

Available related studies and Expected Results: Studies measuring changes to EPCs in type 2 diabetes patients are very limited. To the best of our knowledge there are no studies examining the effect of saxagliptin in early diabetes on patient's CD34/KDR+ve cells and comparing that to the effect of lifestyle + metformin on CD34+ve cell population. The regenerative potential of EPC is thought to be due to direct incorporation into vascular endothelium and/or the secretion of angio-supportive factors to enhance endothelial repair and function^{17, 18, 19}. Our studies and others^{11, 12, 34}, have shown that various disease states, including those seen in diabetes, can deplete and damage EPC, thereby diminishing their regenerative potential. The inability to maintain or repair damaged endothelial tissue leads to cumulative vascular dysfunction and cardiovascular disease.

We hypothesize that monitoring *number, function and gene expression of endothelial progenitors will allow us to quantify cardiovascular disease risk at the onset and regenerative potential post intervention at a cellular level. It will also help us to identify and correlate the best endothelial function bio-chemical inflammatory marker as an early indicator of cardiovascular disease progression in early type 2 diabetes.*

Therefore, studying the effects of Saxagliptin which can increase SDF1 alpha levels and possibly CXCR4 receptor expression as an intervention on the number and health of EPCs may not only provide insight on the biological role of these cells, but they can be used as a tool to study vascular biology and lastly can be a potential target for prevention of diabetes vascular complications.

We expect to establish that saxagliptin improves endothelial function that is EPC number, function, gene expression and bio-inflammatory markers beyond its glycemic control effect in type 2 diabetes patients.

Saxagliptin 5 mg or placebo will be added to patients who have type 2 diabetes diagnosed less than 8 years with HbA1C of 6 to 9 % (both inclusive) while being on lifestyle modification and Metformin (≥ 1.0 to ≤ 2 gm/d orally).

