5.7 Treatment Compliance

Subjects will be given study drug at each dispensing visit with enough study drug to last until the next visit. The subjects will return all unused medication and compliance will be assessed. Subjects will be in compliance if they have taken at least 75% of study drug.

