6 STUDY ASSESSMENTS AND PROCEDURES

6.1 STUDY SCHEMATIC

6.2 TIME AND EVENTS SCHEDULE

Time and Events Schedule for Protocol

Procedure	Screening Visit (Week -4)	Baseline/ Randomization Visit 1 (Week 0)	During Treatment Visit 2 (Week 6)	End-of-Treatment Visit 3 (Week 12)
Eligibility Assessments				
Informed Consent		X		
Inclusion/Exclusion Criteria		X		
Medical History		X		
Safety Assessments				
Physical Examination	X			X
Targeted Physical Examination		X	X	X

Time and Events Schedule for Protocol

Procedure	Screening Visit (Week -4)	Baseline/ Randomization Visit 1 (Week 0)	During Treatment Visit 2 (Week 6)	End-of-Treatment Visit 3 (Week 12)
Vital Signs (BP, RR, Temp, HR)	X	X	X	X
Assessment of Signs and Symptoms		X	X	X
Adverse Events Assessment	X	X	X	X
Laboratory Tests (Biochemical)	screening	X	X	X
Pregnancy Test (if applicable)	X	X	X	X
Efficacy Assessments				
Peripheral blood draw for CD34+cell harvest		X	X	X
Pulse wave analysis		X	X	X
Pulse wave velocity assessment		X	X	X
Hip / Waist Measurements		X	X	X
Tanita Scale		X	X	X
REE		X	X	X
Clinical Drug Supplies				
Randomize		X		
Dispense Study Treatment		X	X	

Screening visit= week-4; Visit 1= week 0, Visit 2= week 6 and Visit 3= week 12.

+/- 3 day window for visits 1-3

Research Study Design and Methods:

Patient Definition and Selection: Adults aged 40-70 years will be recruited mainly from the MFA research patient database provided by MFA Information Technology. The remaining patients will be recruited from the endocrinology clinic at GWU and referring primary care physicians. Suitable advertisements for the study patient enrollment will be posted. Patients will be included in the study if they have been diagnosed with type 2 diabetes within the previous 8 years using criteria of the American Diabetes Association², and are currently treated with no other hypoglycemic agents other than a stable dose (>3 months) of metformin (≥ 1.0 to ≤ 2 grams daily). We plan to enroll subjects with HbA1C between 6% and 9% (both inclusive) and with BMI 25-34.9 kg/m² (both inclusive). Post enrollment, patients will be randomized to saxagliptin 5 mg or placebo as detailed in Study Design for direct comparison between the two regimens.

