6.2.1 Serious Adverse Event Collecting and Reporting

Following the subject's written consent to participate in the study, all SAEs, whether related or not related to study drug, will be collected, including those thought to be associated with protocol-specified procedures. All SAEs will be collected that occur within 30 days of discontinuation of dosing or within 30 days of the last visit for screen failures. If applicable, SAEs will be collected that relate to any later protocol-specified procedure (e.g., a follow-up skin biopsy).

The investigator will report any SAE occurring after these time periods that is believed to be related to study drug or protocol-specified procedure at 90 days and 180 days period

An SAE report will be completed for any event where doubt exists regarding its status of seriousness.

If the investigator believes that an SAE is not related to study drug, but is potentially related to the conditions of the study (such as withdrawal of previous therapy, or a complication of a study procedure), the relationship will be specified in the narrative section of the SAE Report Form.

All SAEs, whether related or unrelated to saxagliptin, and all pregnancies will be reported to BMS (by the investigator or designee) within 24 hours.

All SAEs should be reported via confirmed facsimile (fax) transmission, or scanned and reported via electronic mail to:

SAE Email Address: [contact]

SAE [contact]

SAEs will be reported on MedWatch Form 3500A, which can be accessed at: <http://www.accessdata.fda.gov/scripts/medwatch/>.

MedWatch SAE forms should be sent to the FDA at:

MEDWATCH
[name]
[name]
Fax: [name] ([name])
<http://www.accessdata.fda.gov/scripts/medwatch/>

All SAEs should simultaneously be faxed or e-mailed to BMS at:

Global Pharmacovigilance & Epidemiology
Bristol-Myers Squibb Company
[contact]
Email: [contact]

If an ongoing SAE changes in its intensity or relationship to study drug or if new information becomes available, a follow-up SAE report should be sent within 24 hours to the BMS using the same procedure used for transmitting the initial SAE report. All SAEs should be followed to resolution or stabilization.

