6.2.2 Non-Serious Adverse Events (NSAEs) Collecting and Reporting

The collection of non-serious adverse event (NSAE) information will begin at initiation of study drug. NSAE information will be collected from the start of a placebo lead-in period or other observational period intended to establish a baseline status for the subjects. NSAEs will be followed to resolution or stabilization, or reported as SAEs if they become serious. Follow-up as required for NSAEs that cause interruption or discontinuation of study drug, or those that are present at the end of study treatment as appropriate will be undertaken. All identified NSAEs will be documented appropriately.

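### Adverse events are to be followed until 30 days after the last dose, but the schedule lists no adverse-event contact after week 12; one telephone call would cover the window (minor)

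*Combined protocol and SAP*

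**What the plan says.** **The window.** Section 5.9 has AEs "evaluated on a continuous basis while the patient is on study and until 30 days after the last dose of study drug". Section 6.2.1 adds, for SAEs whether or not related to study drug: "All SAEs will be collected that occur within 30 days of discontinuation of dosing".

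**The visits.** The schedule in section 6.2 marks AE assessment at weeks -4, 0, 6 and 12 and has no later column. Its key reads "Screening visit= week-4; Visit 1= week 0, Visit 2= week 6 and Visit 3= week 12". The synopsis, under Criteria for Evaluation, has patients screened and "then evaluated for end points at weeks 0, 6 and 12". The note beside the schema in section 4.1 allows plus or minus "3 days for visits Wk 0 Wk 6 and Wk 12, if the particular day is not feasible".

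**The last dose.** The schedule marks dispensing at weeks 0 and 6 only, and section 5.7 says "Subjects will be given study drug at each dispensing visit with enough study drug to last until the next visit". For completers, dosing therefore ends at about week 12.

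**Other follow-up.** Section 5.9 follows treatment-related AEs until they recover or are judged irreversible. Section 6.2.2 says "NSAEs will be followed to resolution or stabilization, or reported as SAEs if they become serious". Section 6.2.1 has the investigator report SAEs that arise after the 30 days and are "believed to be related to study drug or protocol-specified procedure at 90 days and 180 days period". Section 6.2 (Collection and Reporting) accepts events that patients volunteer as well as events brought out by open questioning.

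**The concern.** The protocol set itself a 30-day safety window, but its schedule stops where that window opens for completers. No planned occasion exists to ask about new events, so a record of no events in those 30 days could mean that none occurred or that nobody asked.

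Three features of the plan give the window some content:

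- The week-12 visit includes an 85 mL blood draw, and section 6.2.1 wants SAEs linked to protocol procedures. A delayed effect of that last draw would arise after the last AE check.
- Section 4.2.1 asks women of child-bearing potential to use contraception for up to 4 weeks after the last dose, and section 6.1.1 handles pregnancy as an SAE. The last scheduled pregnancy test is at week 12.
- There is no data monitoring committee (section 7), so ascertainment rests with the site.

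What is at stake is how complete safety ascertainment is after treatment. The efficacy analysis is not involved.

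**Working it through.** The plan gives no figure to reproduce. The check compares the promised window with the last scheduled assessment, in days.

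**Inputs**

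- Treatment duration: 12 weeks (section 4.1), so 12 × 7 = 84 days.
- Week-12 visit day *v*: 84, or 81 to 87 with the 3-day allowance.
- Window: 30 days after the last dose (sections 5.9 and 6.2.1).
- Day of last dose: *d*.

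**Formula.** The window closes on day *d* + 30. If *v* is the last visit attended on or after day *d*, then

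uncovered days = max(0, *d* + 30 − *v*).

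If no visit is attended after dosing stops, all 30 days are uncovered.

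**Completers**

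- With the last dose on the visit day, *d* = *v* and 30 days are uncovered, whatever *v* is. The window closes on day 84 + 30 = 114 (111 to 117 with the allowance).
- If dosing ended on day 84 and the visit slipped to day 87, then 84 + 30 − 87 = 27 days are uncovered.
- As a share of the period from first dose to window close, this is 30 / 114 = 26%.

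**Early stoppers**

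| Case | Uncovered days |
|---|---|
| Attends week 12 on day 84 | max(0, *d* − 54) |
| Example: stops day 70, attends day 84 | 70 + 30 − 84 = 16 |
| Stops by day 54, attends day 84 | 0 |
| Attends no further visit | 30 |

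The day-54 threshold is 84 − 30. With the visit allowance it runs from 81 − 30 = 51 to 87 − 30 = 57.

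The rows that assume week-12 attendance are conditional. Section 4.2.3 asks patients who discontinue to follow the procedures in Section 6. It does not name week 12, the schedule has no early-termination visit, and two sections in the body carry the number 6 (Study Assessments and Procedures; Adverse Event Reporting).

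**Does other text schedule a contact?** Follow-up under sections 5.9, 6.2.1 and 6.2.2 concerns events already known. The 90- and 180-day wording covers related SAEs after the 30 days and names no patient contact. None of these provides a planned occasion to ask every patient about new events.

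**The case against.** The strongest reply is that nothing here conflicts. Section 6.2 accepts spontaneous reports, so a window served that way is allowed, and preferring a call is an operational choice. It is true that there is no conflict. A reader might infer that the 30-day rule and the schedule contradict each other, and the documents do not support that.

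A reader might also infer that new events could come to light only by spontaneous report. That goes too far, for three reasons:

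- The schedule is not a full list of contacts. The lifestyle section has the coordinator downloading accelerometer data at regular intervals, with no row in the table.
- Following an open AE could bring out a new one.
- The 90- and 180-day wording is ambiguous. If it means planned look-backs, these could also reveal events from the first 30 days.

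Sections 5.9 and 6.2.1 are also instructions in their own right. The missing row leaves the occasion unspecified and does not show that the site would do nothing. The schema figures are not shown and the consent pages were removed, so a reporting instruction or a follow-up contact may appear there.

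Finally, the stakes are low. Half-lives are 2.5 h for saxagliptin and 3.1 h for its metabolite (sections 1.1.3.1 and 1.1.3.4). At six half-lives, the multiple used in section 6.5, the metabolite takes 6 × 3.1 = 18.6 h to clear. Safety is not a stated objective in section 2.

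What survives is narrower: a window the protocol chose has no scheduled contact for completers, and none of the replies supplies one.

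**Conclusion.** The point holds as a minor, cheap improvement. For completers, no AE contact is scheduled in about 30 of the 30 days after the last dose (27 if the visit falls 3 days after dosing ends), and finding new events relies mainly on spontaneous report. For early stoppers the gap runs from 0 to 30 days, depending on when they stop and whether they attend week 12.

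This assumes that dosing ends at about the week-12 visit and that no contact is described in the material that is not shown. The day counts describe scheduled contact only. It would be tempting to conclude that events will be missed or that the safety comparison is biased. The documents give no basis for a number of missed events, and the schedule is the same in both arms. The efficacy analysis and sample size are unaffected.

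**What to change.** Keep the 30-day window. Add one line to the Time and Events Schedule: a telephone contact by the existing research coordinator 30 days after the last dose (about day 114 for a completer), for every patient whose window is not already covered by a visit. It should record new AEs, SAEs and pregnancies, and the status of open events. Open-ended questions keep to the rule in sections 6.1 and 6.2 against asking about specific events.

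The cost is about 36 short calls if made to the planned completers (2 × 18) and at most 42 if made to everyone enrolled (2 × 21), plus a protocol revision reviewed by the IRB under section 9.1.1. No visit, procedure or blood draw is added. For each patient reached, the uncovered period falls from up to 30 days to 0.

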6 ADVERSE EVENT REPORTING

6.1 Adverse Events

An ***Adverse Event (AE)*** is defined as any new untoward medical occurrence or worsening of a pre-existing medical condition in a patient or clinical investigation subject administered an investigational (medicinal) product and that does not necessarily have a causal relationship with this treatment. An AE can therefore be any unfavorable and unintended sign (including an abnormal laboratory finding, for example), symptom, or

disease temporally associated with the use of investigational product, whether or not considered related to the investigational product.

The causal relationship to study drug is determined by a physician and should be used to assess all adverse events (AE). The causal relationship can be one of the following:

Related: There is a reasonable causal relationship between study drug administration and the AE.

Not related: There is not a reasonable causal relationship between study drug administration and the AE.

The term "reasonable causal relationship" means there is evidence to suggest a causal relationship.

Adverse events can be spontaneously reported or elicited during open-ended questioning, examination, or evaluation of a subject. (In order to prevent reporting bias, subjects should not be questioned regarding the specific occurrence of one or more AEs.)

6.1.1 Serious Adverse Events

A **Serious Adverse Event (SAE)** is any untoward medical occurrence that at any dose:

- results in death
- is life-threatening (defined as an event in which the subject was at risk of death at the time of the event; it does not refer to an event which hypothetically might have caused death if it were more severe)
- requires inpatient hospitalization or causes prolongation of existing hospitalization (see note below for exceptions)
- results in persistent or significant disability/incapacity
- is a congenital anomaly/birth defect
- is an important medical event, defined as a medical event that may not be immediately life-threatening or result in death or hospitalization but, based on appropriate medical and scientific judgment, may jeopardize the subject or may require intervention (e.g., medical, surgical) to prevent one of the other serious outcomes listed above. Examples of such events include but are not limited to intensive treatment in an emergency department or at home for allergic bronchospasm; blood dyscrasias or convulsions that do not result in hospitalization. Potential drug induced liver injury (DILI) is also considered an important medical event (see Section 7.6 for the definition of potential DILI)

Suspected transmission of an infectious agent (e.g., any organism, virus or infectious particle, pathogenic or non-pathogenic) via the study drug is an SAE.

Although pregnancy, overdose and cancer are not always serious by regulatory definition, these events must be handled as SAEs (See Section 7.5 for reporting pregnancies).

NOTE: The following hospitalizations are not considered SAEs:

- a visit to the emergency room or other hospital department lasting less than 24 hours that does not result in admission (unless considered an “important medical event” or a life-threatening event)
- elective surgery planned before signing consent
- admissions as per protocol for a planned medical/surgical procedure
- routine health assessment requiring admission for baseline/trending of health status (e.g., routine colonoscopy)
- medical/surgical admission for purpose other than remedying ill health state that was planned before study entry. Appropriate documentation is required in these cases.
- admission encountered for another life circumstance that carries no bearing on health status and requires no medical/surgical intervention (e.g., lack of housing, economic inadequacy, caregiver respite, family circumstances, administrative).

6.1.2 Non-serious Adverse Events

Non-serious adverse events are all adverse events that are not classified as SAEs.

6.1.3 Adverse Events of Special Interest

In this study, the following adverse events are to be reported to AstraZeneca, regardless of whether these reports are classified as serious or unexpected:

1. liver test abnormalities accompanied by jaundice or hyperbilirubinemia
2. opportunistic infections associated with the use of saxagliptin
3. pancreatitis
4. anaphylaxis
5. angioedema
6. Steven-Johnson’s Syndrome

6.2 Collection and Reporting

Adverse events can be spontaneously reported or elicited during open-ended questioning, examination, or evaluation of a subject. To prevent reporting bias, subjects should not be questioned regarding the specific occurrence of one or more adverse events.

If known, the diagnosis of the underlying illness or disorder should be recorded, rather than its individual symptoms. The following information should be captured for all AEs: onset, duration, intensity, seriousness, relationship to investigational product, action taken, and treatment required. If treatment for the event was administered, it should be recorded in the medical record. The investigator must supply AstraZeneca and the IRB/IEC with any additional information requested, notably for reported deaths of subjects.

